# 1 BACKGROUND

With the development of the thin-slice and high-resolution computed tomography (CT) and the improvement of people's health consciousness in recent years, more and more small pulmonary nodules (SPNs) have been discovered during routine medical tests. However, the property of the SPNs can hardly be identified only through imaging examination. Accurate pathological diagnosis is essential.

The CT-guided percutaneous needle biopsy of lung and the bronchoscopy biopsy are common means adopted to obtain the histological features of SPNs, but their accuracies are influenced by various factors of the nodules. Therefore, minimally invasive surgery is required to obtain the pathological result of the nodule. In recent years, video-assisted thoracoscopic surgery (VATS) provides effective technical support for the early diagnosis and treatment of pulmonary nodules. However, some pulmonary nodules are too small or too deep to be reached. Therefore, localization and sampling of pulmonary nodules are difficult in some cases. The literature reported that the rate of conversion to thoracotomy was up to 46% due to insufficient localization of pulmonary nodules. Therefore, localization methods for SPNs were invented to solve the problem.

At present, many techniques can be used for pulmonary nodule localization. Representatives include dyeing localization, intraoperative ultrasonic localization, lipiodol, and hookwire, etc. Each method has its own disadvantages. The dyeing localization technique is rarely adopted due to its high incidence rate of complications. As for intraoperative ultrasonic localization, accurate localization can hardly be achieved due to the existence of pulmonary alveoli, and largely depends on the experience of the operator. The lipiodol labeling technique requires finger palpation to find the nodule and may result in lung tissue damage. The indication approved by the Chinese Food and Drug Agency (CFDA) of the hookwire is for breast tumor localization. However, many doctors worldwide have performed clinical studies on using the hookwire for SPNs localization and reported good results in the literature, which indicated that hookwire is a convenient localization method for SPNs with high accuracy. However, according to some literature, hookwire also has many complications. Therefore, a more safe and effective localization technique is needed.

We have recently developed a new device that has a four-hook anchor with scaled sutures, and demonstrated a high success rate, good tolerance of patients, and low rate of complications for preoperative localization of SPNs in a multi-center clinical trial. However, the effectiveness and safety between the new device and hookwire are still unclear. Here we conduct a randomized clinical trial to compare the two localization devices.

# 2. EXPERIMENTAL PRODUCT CHARACTERISTICS, MECHANISMS AND TRIAL SCOPE

#### 2.1 Product Characteristics

The disposable pulmonary nodule localization needle is mainly comprised of a puncture needle, a pushing tube, an anchor claw, a suture and a protective tube. The puncture needle is comprised of a needle tube, a handle and a buckle. The distal end of the suture is connected to the anchor claw. The proximal end of the suture is inside the pushing tube. The suture is divided into three parts by three colors. Relevant structures are shown in **Figure 1**.

[figure not shown]

Figure 1 The structure of the novel localization device.

#### 2.2 Product Mechanisms

The disposable pulmonary nodule localization needle is mainly comprised of a puncture needle, a pushing tube, an anchor claw, a suture and a protective tube. Guided by CT, the puncture needle inserts through the chest wall and the lung, and reaches the edge of the pulmonary nodule. Then the pushing system releases the anchor claw which hooks up the pulmonary tissue. In the resection surgery later, the scale on the suture can be used for estimating the depth.

# 2.3 Trial Scope

Patients who accept the surgery for pulmonary nodule localization.

#### 3 EXPERIMENTAL PRODUCT INDICATION

Pulmonary nodule localization.

#### 4 CONTENTS AND OBJECTIVES OF THE TRIAL

#### 4.1 Trial Contents

The trial is performed to evaluate the safety and efficacy of a novel disposable pulmonary nodule localization needle produced by Ningbo Senscure Biotechnology Co., Ltd versus hookwire which is a classic disposable pulmonary nodule localization needle. About 409 patients who are suitable for pulmonary nodule resection by surgery are enrolled according to the inclusion/exclusion criteria of the trial. Localization is performed using the pulmonary nodule localization needle under the guidance of CT before the resection. Then the pulmonary nodule is resected by VATS. The successful localization rate, adverse events (mainly refer to complications of localization), the pain scoring and the localization time during the trial are calculated and compared.

# 4.2 Trial Objectives

Evaluate and compare the safety and efficacy of the novel localization device versus hookwire for thoracoscopic resection of SPNs.

#### • Primary objective

Evaluate and compare the successful localization probability of the novel localization device and hookwire for pulmonary nodules.

#### Secondary objective

Evaluate and compare the adverse events probability, the localization time, and the pain degree of the novel localization device and hookwire.

#### **5 SCOPE OF SUBJECTS**

#### 5.1 Inclusion Criteria

- (1) 18 years old  $\leq$  Age  $\leq$  80 years old, of either sex;
- (2) Patients who are confirmed to have pulmonary nodules (diameter ≤1 cm, solid or ground-glass nodules) by chest CT examination and expected to receive wedge resection or segmentectomy of the lung by VATS;
- (3) Significantly enlarged lung hilus or mediastinal lymph node is not observed by CT examination of the chest;

- (4) Performance status (PS): PS scale under 3;
- (5) Patients who voluntarily participate in and sign the informed consent form (ICF).

#### 5.2 Exclusion criteria

- (1) Patients who are not suitable for localization before surgery based on the judgment of the investigator, e.g., patients who have pleural effusion or severely damaged lung tissue;
- (2) Systemic factors: sepsis, repeated pulmonary infection, any type of severe infectious diseases 1 month before surgery;
- (3) Patients having severe diseases of heart, brain, lung, liver and kidney or severe hypertension;
- (4) Patients having severe coagulation disorders;
- (5) Patients having any distant metastasis;
- (6) Patients who participate in the clinical trial of other drugs or medical devices within 30 days before screening;
- (7) Other conditions which are considered as inappropriate for this clinical trial.

#### 6 CLINICAL EVALUATION CRITERIA

# 6.1 Evaluation Criteria of Efficacy

#### • Successful localization rate

Successful localization is defined as: the localization device is released and located in or around the nodule (within 10 mm to the edge of the nodule), and no dislodgement of the device occurred from the localization procedure to the first exploration of VATS. Moreover, no fault or fracture of the device is observed during the whole procedure.

If the localization needle should be changed during the study (for single or multiple nodules), the change information must be recorded. Localization evaluation is performed for all the used products. For multiple nodules (using multiple localization needles), localization is considered as a failure if the localization of one site fails.

# 6.2 Evaluation Criteria of Safety

Adverse events during the trial mainly refer to complications of localization caused by percutaneous lung puncture, mainly including:

• Pneumothorax: Air enters into the pleural cavity due to puncture and results in pneumatosis. Evaluation method: CT examination is performed before the end of localization to find whether there is any extremely

low-density air shadow in the pleural cavity near the puncture needle and whether lung tissue is compressed and shrunk to varying degrees. Pneumothorax is classified into small pneumothorax (<20%), medium pneumothorax (20%–40%) and large pneumothorax (>40%) according to the collapse degree of the lung. Pneumothorax caused by puncture generally belongs to small pneumothorax and does not require any special treatment.

- Hemorrhage: refer to pulmonary bleeding caused by a puncture. Evaluation method: CT examination is performed before the end of localization to find whether there is any diffuse or nodular shadow over the tissue around the puncture site. Bleeding exists if yes. Bleeding caused by puncture is generally shown as a flaky, cloud- or cotton-shaped effusion shadow or the effusion shadow along the needle passage. No special treatment is needed because the bleeding amount is small.
- Pleural reaction: Pleural reaction refers to a series of reactions in the process of a pleural puncture due to the diagnosis or treatment of thoracic diseases, such as cough, dizziness, chest tightness, pale complexion, sweating and even fainting. In case of pleural reaction, stop the puncture immediately, put the patient in a supine position, keep the patient warm, and observe the changes of pulse, blood pressure and consciousness. Those with mild symptoms can relieve themselves after rest. For patients with obvious sweating and low blood pressure, oxygen inhalation and 10% glucose supplement of 500 ml were given. If necessary, inject adrenaline subcutaneously to prevent shock.

#### 6.3 Evaluation Criteria of Usability

The following indexes are used to evaluate the usability of the localization needle:

- Localization: Pushing ability, penetration ability, ease of use, withdrawal performance and successful release or not, etc.
- Nodule resection: whether the suture is detectable and fractured, and whether the anchor claw shifts and unhooks, etc.

When more than one localization needles are used for a single lesion, the poorest performance evaluation is recorded.

# 7 OVERALL DESIGN OF THE TRIAL

#### 7.1 Trial Design

This randomized clinical trial is designed as a parallel, prospective, open-label study. The intervention group is the novel localization device, and the control group is hookwire which is a classic localization device. The

study area is located in the Department of Thoracic Surgery of Shanghai Chest Hospital.

#### • Primary endpoint

The localization success probability of the novel localization device and hookwire for pulmonary nodules.

#### • Secondary endpoints

- (1) The probability of pneumothorax, hemorrhage, the pleural reaction of the novel localization device and hookwire;
- (2) The pain degree caused by the novel localization device and hookwire, measured by the visual analog scale (VAS);
- (3) The time required for the localization procedure of the novel localization device and hookwire.

#### 7.2 Randomization Methods

We use the Stata 14 software (StataCorp, Texas, USA) to produce the randomization number, which will be allocated to the patients signed the informed consent by our investigators. According to the number, the patients are randomized allocated into the different study groups. Both the surgeons, the radiologists, and the patients were masked as to the allocation schedule. Sealed and numbered envelopes that contained the allocated group for each patient were prepared and opened at the beginning of each localization procedure.

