#### 7.6 Localization Methods

CT-guided localization is arranged before pulmonary nodule resection. Firstly, chest CT scanning is performed. Guided by CT image, the operator selects the appropriate position and puncture site and determines the best insertion angle and path. After local anesthesia, the localization device is used. The usage is as follows:

- (1) Open the inner package, take out the localization needle, and remove the protective tube;
- (2) Confirm the position of the pulmonary nodule through CT image, and insert the localization needle into the chest wall and lung to reach the edge of the pulmonary nodule under CT guidance;
- (3) Remove the release buckle from the localization needle, push the pushing tube to the bottom, so as to release the anchor claw from the needle tube. The anchor claw will be located around the nodule (within 10 mm to the edge of the nodule);
- (4) Withdraw the puncture needle from the pulmonary nodule edge to the pleural cavity;
- (5) Completely pull the pushing tube out of the localization needle, then put the pushing tube back to the localization needle, and push the pushing tube to the bottom, so that the proximal end of the suture is pushed into the chest wall;

(6) Remove the localization device, press on the puncture point with sterile gauze to stop any possible bleeding, and send the patient to the operating room.

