#### 8.4 Expected Duration of Each Subject

The expected duration of each subject is 1 week.

After admission, the investigator informs the patient of the trial, i.e., the informed consent process. The patient signs the ICF. The investigator screens the patient strictly as per inclusion & exclusion criteria of the protocol. The qualified patient will receive nodule resection surgery. Localization using the investigational medical device will be performed before surgery. Whether the localization is accurate or not can be determined by CT examination upon puncture (the endpoint measurement of effectiveness is the successful localization rate). The nodule resection surgery will be conducted immediately after localization. The localization needle will be removed together with the resected tissue in the surgery. Usability and safety of the device are also observed in the process. The duration is about 1 week.

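### Envelope opening is not tied to a completed suitability decision on the planning CT, so a patient could be dropped from the primary analysis with the arm known

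*Protocol*

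**What the plan says.** All references are to the protocol.

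- **Section 7.2** gives the randomization number, "which will be allocated to the patients signed the informed consent by our investigators". It says who receives a number but not at what moment. It also says: "Both the surgeons, the radiologists, and the patients were masked as to the allocation schedule". On opening: "Sealed and numbered envelopes that contained the allocated group for each patient were prepared and opened at the beginning of each localization procedure".
- **Section 7.6** describes the localization method in order: "Firstly, chest CT scanning is performed. Guided by CT image, the operator selects the appropriate position and puncture site". The insertion angle and path are chosen next, then comes local anesthesia, then the device. The envelope is not mentioned.
- **Section 5.2**, exclusion (1), covers "Patients who are not suitable for localization before surgery based on the judgment of the investigator", with pleural effusion and severely damaged lung tissue as examples. Exclusion (7) reads: "Other conditions which are considered as inappropriate for this clinical trial".
- **Section 8.4** places the eligibility check after consent and before localization: "The investigator screens the patient strictly as per inclusion & exclusion criteria of the protocol". Table 1 in section 7.5 ticks eligibility at V1 only (day -7 to 0), and ticks CT at both V1 and the localization visit.
- **Section 7.1** makes the trial open-label.
- **Section 11.1** analyses the primary and secondary endpoints in the SAS, which requires use of the device and at least one safety record. Section 11.7 plans no sensitivity analysis.

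**The concern.** Sealed envelopes protect the comparison only if the decision to keep a patient is closed before the envelope is opened. Here the scan on which the puncture is planned is taken at the localization visit, up to a week after the eligibility check, and the text ties opening to the start of that same procedure. If the envelope is opened first, the operator judges the new scan with the device known.

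A patient set aside at that moment has not used a device and so is not in the SAS. If lesions that look hard to localize were set aside more readily in one arm, the success rates would be compared between groups that randomization no longer balances. No planned analysis would show it.

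**Working it through.** **1. The sequence, section by section**

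| Step | Source | Device known? |
|---|---|---|
| Consent, then eligibility check with CT (V1) | 8.4, Table 1 | No, schedule masked (7.2) |
| Number given to consented patients | 7.2, moment not stated | No, envelope sealed |
| Envelope opened at the start of localization | 7.2 | Yes, from here on |
| New chest CT; site, angle and path chosen | 7.6, Table 1 | Order against opening not stated |
| Local anesthesia, then device | 7.6 | Yes |

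The third and fourth rows both claim the start of the procedure. Staff who follow 7.2 literally open the envelope first. No sentence says that eligibility is final before opening, and none provides for a repeat check at localization.

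**2. What happens to a patient dropped in between**

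The SAS requires device use, so this patient is not counted in the primary endpoint. The FAS might keep the patient, but 11.1 uses it only for baseline data.

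**3. Possible size (illustration)**

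The plan gives no figure on this point. Inputs from section 11.2 are 136 control and 273 intervention patients (116/0.85 = 136.5; 232/0.85 = 272.9), Fisher's exact test, one-sided, 0.05. Assumptions:

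- true success p is equal in both arms, at 89% (the plan's hookwire rate) or 93% (midway between the plan's 89% and 97%);
- a share k of the novel arm only is removed after opening;
- a fraction f of those removed would have failed.

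The remaining novel arm has n = 273(1 − k) and apparent success q = (p − k(1 − f))/(1 − k). For k = 3%, n = 273 × 0.97 ≈ 265. At p = 0.93:

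- f = 0.5: q = (0.93 − 0.015)/0.97 = 0.943
- f = 1: q = 0.93/0.97 = 0.959

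Summing the exact Fisher rejection probability over both binomial distributions gives the type I error:

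| Removal from novel arm | p = 89% | p = 93% |
|---|---|---|
| None | 3.6% | 3.2% |
| 1–3%, unrelated to outcome (f = 1 − p) | 3.5–3.6% | 3.3–3.5% |
| 1%, all would have failed | 6.3% | 7.0% |
| 3%, half would have failed | 7.6% | 9.5% |
| 3%, all would have failed | 17.7% | 26.3% |

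**4. How much foresight this needs**

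The operator would have to pick out a share kf/(1 − p) of all novel-arm failures from the scan:

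- 1%, all failing: 0.01/0.11 = 9% to 0.01/0.07 = 14%
- 3%, half failing: 0.015/0.11 = 14% to 0.015/0.07 = 21%
- 3%, all failing: 0.03/0.11 = 27% to 0.03/0.07 = 43%

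**5. If every opened envelope is analysed**

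With unpunctured novel-arm patients counted as failures, that arm's success becomes p − k(1 − f), which is never above p (for p = 0.93, k = 0.03, f = 0.5: 0.93 − 0.015 = 0.915). In this scenario the type I error cannot then exceed its value without removal.

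**The case against.** The strongest reply is that the protocol already settles eligibility while allocation is masked. Table 1 ticks inclusion and exclusion at V1 only, section 8.4 sends the qualified patient on to localization, and no text invites anyone to reapply section 5.2 on the day. This stands: exclusion after opening is a gap left open, not a step that the protocol provides for.

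Three stronger readings are tempting but not supported:

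- *The envelope is opened before the planning CT.* This is inferred from 7.2 and 7.6 together. Neither states the order.
- *Numbers are given at consent, so the order of steps is wrong.* Section 7.2 says who gets a number, not when, and a number tied to a sealed envelope does not reveal the device.
- *No choice of analysis set could repair it.* Step 5 shows that counting every opened envelope, with unpunctured patients as failures, removes the inflation calculated here.

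It is also fair to say that the named examples in exclusion (1), effusion and damaged lung, are not device-specific. Section 6.1 counts dislodgement and device fault or fracture as failures, which a scan before puncture does not show. That makes the upper end of the illustration hard to reach.

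What remains is that no sentence requires suitability on the day's scan to be recorded before opening, and that the SAS would remove the patient from the endpoint without trace. Envelope timing is a conduct rule that the protocol itself fixes, so it is not a detail left to a statistical analysis plan.

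**Conclusion.** The point holds as a gap in procedure. The protocol does not require the suitability decision on the planning CT to be closed before the device is revealed, and its endpoint set leaves out anyone withdrawn between opening and device use.

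The size is unknown because the documents give no rate of such withdrawals. The range of 6% to 26% rests on removal from the novel arm only and on removed patients failing far more often than average. Without that link to outcome the error stays at 3.2% to 3.6%, below the nominal 5%. A reader might infer that the trial's type I error is in fact inflated; the documents do not support that. This is a cheap improvement worth making, not an error that invalidates the design.

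**What to change.** In section 7.2, replace the stated time of opening with: *after the planning CT has been read and the operator has recorded, with time, that the patient remains eligible and suitable for localization, and before local anesthesia*.

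Add that once the envelope is opened the patient stays in the primary analysis in the allocated arm, with the scoring of an unpunctured patient fixed in advance, and that this does not limit the clinical decision not to puncture. Section 11.1 must be aligned, since the SAS as defined would still drop such a patient. The later opening is the main remedy: a scoring rule alone would still let the number of unpunctured patients differ by arm.

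Cost: a few sentences, one timed tick box on the CRF, and both devices ready in the CT room. The planned 409 patients do not change.

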# 7.3 Investigational Product

Product name: Disposable pulmonary nodule localization needle

Manufacturer: Ningbo Senscure Biotechnology Co., Ltd.

Product specifications & model: SS510-10

#### 7.4 Number of Cases

At least 409 cases.

#### 7.5 Trial Process

This trial includes the following periods: (see **Table 1**)

- (1) Case screening;
- (2) Case enrollment;
- (3) Localization;
- (4) Surgery.

Table 1 The detail periods and recording items of the clinical trial.

Item	Screening period	Localization	Surgery
Item	sereening period	Eocanzation	Suigery

Times of visit	V1	V2	V3
Number of days	-7-0 day		0 day
Sign the ICF	×		
Inclusion/exclusion	×		
criteria	^		
History	×		
Demographic data	×		
Physical examination	×		
Vital signs	×	×	×
СТ	×	×	
AE record	×	×	×

Remarks: Vital signs: Blood pressure, heart rate, respiration, pulse and chest examination, etc.

#### 7.6 Localization Methods

CT-guided localization is arranged before pulmonary nodule resection. Firstly, chest CT scanning is performed. Guided by CT image, the operator selects the appropriate position and puncture site and determines the best insertion angle and path. After local anesthesia, the localization device is used. The usage is as follows:

- (1) Open the inner package, take out the localization needle, and remove the protective tube;
- (2) Confirm the position of the pulmonary nodule through CT image, and insert the localization needle into the chest wall and lung to reach the edge of the pulmonary nodule under CT guidance;
- (3) Remove the release buckle from the localization needle, push the pushing tube to the bottom, so as to release the anchor claw from the needle tube. The anchor claw will be located around the nodule (within 10 mm to the edge of the nodule);
- (4) Withdraw the puncture needle from the pulmonary nodule edge to the pleural cavity;
- (5) Completely pull the pushing tube out of the localization needle, then put the pushing tube back to the localization needle, and push the pushing tube to the bottom, so that the proximal end of the suture is pushed into the chest wall;

(6) Remove the localization device, press on the puncture point with sterile gauze to stop any possible bleeding, and send the patient to the operating room.

